3 - Severe Weakness	xx (xx.x%)	xx (xx.x%)	xx(xx.x%)	xx (xx.x%)	xx (xx.x%)	xx (xx.x%)
4 - Paralysis	xx (xx.x%)	xx (xx.x%)				
Deep Tendon Reflexes						
0 - Normal	xx(xx.x%)	xx(xx.x%)	xx(xx.x%)	xx(xx.x%)	xx(xx.x%)	xx(xx.x%)
1 - Ankle reflex reduced	xx(xx.x%)	xx(xx.x%)	xx(xx.x%)	xx(xx.x%)	xx(xx.x%)	xx(xx.x%)
2 - Ankle reflex absent	xx(xx.x%)	xx(xx.x%)	xx(xx.x%)	xx(xx.x%)	xx(xx.x%)	xx(xx.x%)
3 - Ankle reflex absent and knee reflex reduced	xx (xx.x%)	xx (xx.x%)				
4 - All reflexes (both ankle and knee) absent	xx (xx.x%)	xx (xx.x%)				

. . .

Note: Percentages for each Score are n/Number of subjects by treatment group at each visit*100

Reference Listing: 16.2.9.7

- Include the following timepoints: Baseline, Day 1, Week 2, Week 4, Week 6, Week, 8, Week 10, Week 12, and Week 18.
- A column for column for dosing (column for dosing

n = number of subjects by treatment group at each visit for each category; N = number of subjects per treatment group; SDTR = strength and deep tendon reflexes.

^[1] Baseline is defined as the last observation recorded prior to the first dose of treatment.

[figure not shown]
[figure not shown]

Table 14.3.5.9 Summary of Local Injection Site Reactions Safety Population

	Placebo		MEDI7352			Total
Visit/ Statistic or Category	(N=xx)	CCI (N=xx)	CCI (N=xx)	CCI (N=xx)	All MEDI7352 (N=xx)	(N=xx)
Day 1: 15 Minutes after Start of Infusion Subjects with injection Site Assessed	xx (xx.x%)	xx (xx.x%)	xx (xx.x%)	xx (xx.x%)	xx (xx.x%)	xx (xx.x%)
Pain						
None	xx (xx.x%)	xx (xx.x%)	xx (xx.x%)	xx (xx.x%)	xx (xx.x%)	xx (xx.x%)
Mild	xx (xx.x%)	xx (xx.x%)	xx (xx.x%)	xx (xx.x%)	XX (XX.X%)	XX (XX.X%) XX (XX.X%)
Moderate	xx(xx.x%)	$XX (XX.X^{\prime}0)$ $XX (XX.X^{\prime}0)$	xx (xx.x%)	xx(xx.x%)	XX (XX.X%)	xx(xx.x%)
Severe	xx (xx.x%)	xx (xx.x%)	xx (xx.x%)	xx (xx.x%)	xx (xx.x%)	xx (xx.x%)
Tenderness						
None	xx(xx.x%)	xx(xx.x%)	xx(xx.x%)	xx(xx.x%)	xx(xx.x%)	xx(xx.x%)
Mild	xx (xx.x%)	xx(xx.x%)	xx(xx.x%)	xx (xx.x%)	xx(xx.x%)	xx(xx.x%)
Moderate	xx(xx.x%)	xx(xx.x%)	xx(xx.x%)	xx(xx.x%)	xx(xx.x%)	xx(xx.x%)
Severe	xx (xx.x%)	xx (xx.x%)	xx (xx.x%)	xx (xx.x%)	xx (xx.x%)	xx (xx.x%)
Erythema/Redness						
None	xx(xx.x%)	xx(xx.x%)	xx(xx.x%)	xx(xx.x%)	xx(xx.x%)	xx(xx.x%)
Mild	xx(xx.x%)	xx(xx.x%)	xx(xx.x%)	xx(xx.x%)	xx(xx.x%)	xx(xx.x%)
Moderate	xx(xx.x%)	xx(xx.x%)	xx(xx.x%)	xx(xx.x%)	xx(xx.x%)	xx(xx.x%)
Severe	xx (xx.x%)	xx (xx.x%)	xx (xx.x%)	xx (xx.x%)	xx (xx.x%)	xx (xx.x%)

Draft 1.1 | 31-Aug-2023 | Page 103 of 209

Induration/ Swelling

...

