None	xx(xx.x%)	xx(xx.x%)	xx(xx.x%)	xx(xx.x%)	xx(xx.x%)	xx(xx.x%)
Mild	xx(xx.x%)	xx(xx.x%)	xx(xx.x%)	xx(xx.x%)	xx(xx.x%)	xx(xx.x%)
Moderate	xx(xx.x%)	xx(xx.x%)	xx (xx.x%)	xx(xx.x%)	xx(xx.x%)	xx(xx.x%)
Severe	xx(xx.x%)	xx(xx.x%)	xx(xx.x%)	xx(xx.x%)	xx(xx.x%)	xx(xx.x%)

n = number of subjects by treatment group at each visit for each category; N = number of subjects per treatment group.

Note: Percentages for each Score are n/Number of subjects by treatment group at each visit*100

Reference Listing: 16.2.9.8

Programming Notes:

- Include the following timepoints: Day 1: 15 Minutes Post-Dose, Day 1: 30 Minutes Post-Dose, Day 1: 45 Minutes Post-Dose, Day 1: 1 hour Post-Dose, Day 1: 2 hours Post-Dose, Day 1: 4 hours Post-Dose, Week 2, Week 4, Week 6, Week, 8, Week 10, Week 12, and Week 18.
- A column for column dosing (column dosing (column dosing (column dosing (column dosing dosi

Draft 1.1 | 31-Aug-2023 | Page 104 of 209

[figure not shown]

[figure not shown]
Table 14.3.5.10 Summary of Hypersensitivity/Anaphylactic Reactions Safety Population

	Placebo		MEDI7352			Total
		CCI	CCI	CCI	All MEDI7352	
Statistic or Category	(N=xx)	(N=xx)	(N=xx)	(N=xx)	(N=xx)	(N=xx)
Subjects with any	xx (xx.x%)	xx (xx.x%)				
Hypersensitivity/						
Anaphylaxis						
Highest Severity Grade						
Mild	xx(xx.x%)	xx(xx.x%)	xx(xx.x%)	xx(xx.x%)	xx(xx.x%)	xx(xx.x%)
Moderate	xx(xx.x%)	xx(xx.x%)	xx(xx.x%)	xx(xx.x%)	xx(xx.x%)	xx(xx.x%)
Severe	xx (xx.x%)	xx (xx.x%)				
Type of Reaction						
Urticaria	xx(xx.x%)	xx(xx.x%)	xx(xx.x%)	xx(xx.x%)	xx(xx.x%)	xx(xx.x%)
Pruritus	xx(xx.x%)	xx(xx.x%)	xx(xx.x%)	xx (xx.x%)	xx(xx.x%)	xx (xx.x%)
Rash	xx(xx.x%)	xx(xx.x%)	xx(xx.x%)	xx(xx.x%)	xx(xx.x%)	xx(xx.x%)
Flushing	xx (xx.x%)	xx(xx.x%)	xx(xx.x%)	xx (xx.x%)	xx(xx.x%)	xx (xx.x%)
Swollen Lips, Tongue,	xx(xx.x%)	xx(xx.x%)	xx(xx.x%)	xx(xx.x%)	xx(xx.x%)	xx(xx.x%)
Uvula and/or Vulva						
Dyspnoea	xx(xx.x%)	xx(xx.x%)	xx(xx.x%)	xx(xx.x%)	xx(xx.x%)	xx(xx.x%)
Wheeze-Bronchospasm	xx(xx.x%)	xx(xx.x%)	xx(xx.x%)	xx(xx.x%)	xx(xx.x%)	xx(xx.x%)
Stridor	xx(xx.x%)	xx(xx.x%)	xx(xx.x%)	xx (xx.x%)	xx(xx.x%)	xx(xx.x%)
Hypoxia	xx(xx.x%)	xx(xx.x%)	xx(xx.x%)	xx(xx.x%)	xx(xx.x%)	xx(xx.x%)
Hypotension	xx(xx.x%)	xx(xx.x%)	xx(xx.x%)	xx(xx.x%)	xx(xx.x%)	xx(xx.x%)
Crampy Abdominal Pain	xx(xx.x%)	xx(xx.x%)	xx(xx.x%)	xx(xx.x%)	xx(xx.x%)	xx(xx.x%)
Vomiting	xx(xx.x%)	xx(xx.x%)	xx(xx.x%)	xx(xx.x%)	xx(xx.x%)	xx(xx.x%)
Diarrhoea	xx(xx.x%)	xx(xx.x%)	xx(xx.x%)	xx(xx.x%)	xx(xx.x%)	xx(xx.x%)

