6.5. Other Safety Data

Final 1 2 | 04-Oct-2023 | Page 94 of 218

[figure not shown]

Table 14.3.5.1 Descriptive Summary of Vital Signs Safety Population

Parameter: x	XXXX
--------------	------

	Placebo		MEDI7352			Total
Visit Statistic	(N=xx)	CCI (N=xx)	CCI (N=xx)	CCI (N=xx)	All MEDI7352 (N=xx)	(N=xx)
		· /	· /		· /	· · · · · · · · · · · · · · · · · · ·
Baseline [1]						
n	XX	XX	XX	XX	XX	XX
Mean (SD)	xx.x(xx.xx)	xx.x(xx.xx)	xx.x(xx.xx)	xx.x(xx.xx)	xx.x(xx.xx)	xx.x (xx.xx)
Median	XX.X	XX.X	XX.X	XX.X	XX.X	XX.X
Q1, Q3	XX.X, XX.X	XX.X, XX.X	XX.X, XX.X	XX.X, XX.X	XX.X, XX.X	XX.X, XX.X
Min, Max	XX, XX	xx, xx	xx, xx	xx, xx	xx, xx	xx, xx
Day 1: 15 Minutes Pos	st-					
Dose						
n	XX	XX	XX	XX	XX	XX
Mean (SD)	xx.x(xx.xx)	xx.x(xx.xx)	xx.x(xx.xx)	xx.x(xx.xx)	xx.x(xx.xx)	xx.x (xx.xx)
Median	XX.X	XX.X	XX.X	XX.X	XX.X	XX.X
Q1, Q3	XX.X, XX.X	XX.X, XX.X	XX.X, XX.X	XX.X, XX.X	XX.X, XX.X	XX.X, XX.X
Min, Max	XX, XX	xx, xx	xx, xx	xx, xx	xx, xx	xx, xx
Day 1: 15 Minutes Pos	st-					
Dose CFB						
n	XX	XX	XX	XX	XX	XX
Mean (SD)	xx.x(xx.xx)	xx.x(xx.xx)	xx.x(xx.xx)	xx.x(xx.xx)	xx.x(xx.xx)	xx.x (xx.xx)
Median	XX.X	XX.X	XX.X	XX.X	XX.X	xx.x
Q1, Q3	XX.X, XX.X	XX.X, XX.X	XX.X, XX.X	XX.X, XX.X	XX.X, XX.X	XX.X, XX.X
Min, Max	XX, XX	XX, XX	XX, XX	XX, XX	XX, XX	XX, XX

[figure not shown]
^{. . .}

Note: 'Day 1: 5 minutes after Infusion Completion' time point was only applied to subjects enrolled in Stage 1, with data collected under eCRF versions 4.0 (11DEC2018) or older.

Reference Listing: 16.2.9.1

CFB = Change from Baseline; eCRF = Electronic Case Report Form; n = number of subjects by treatment group at each visit for the parameter; N = number of subjects per treatment group; SD = standard deviation; Q1 = first quartile; Q3 = third quartile.

^[1] Baseline is defined as the last observation recorded prior to the first dose of treatment.

Programming Notes:

- Repeat for Supine Heart Rate, Supine Systolic Blood Pressure, Supine Dia stolic Blood Pressure, Respiratory Rate, Body Temperature, Standing Heart Rate, Standing Systolic Blood Pressure, Standing Dia stolic Blood Pressure.
- After Week 2 (inclusive), Supine measure are taken in sitting position. We will consider them as supine (in resting position) for calculating Change from Baseline (always at supine position).

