		Day 1: 30 Minutes after Start of Infusion	DDMMMYYYY / HH:MM (XX)	XX	XX	XX	XX	
		Week 18	DDMMMYYYY / HH:MM (XX)	ND	ND	ND	ND	XXXXXXXXXXXX

[figure not shown]
ND = Not Done.

Note: Study Day is calculated relative to the date of first dose.

Programming Notes:

- Sort by Treatment Arm/ Subject ID / Visit / Date of assessment
- Include the following timepoints: Day 1: 15 Minutes after Start of Infusion, Day 1: 30 Minutes after Start of Infusion, Day 1: 45 Minutes after Start of Infusion, Day 1: 60 Minutes after Start of Infusion, Day 1: 4 hours after Start of Infusion, Week 2, Week 4, Week 6, Week, 8, Week 10, Week 12, and Week 18.

Final 1 2 | 04-Oct-2023 | Page 183 of 218

Listing 16.2.9.9 Hypersensitivity/Anaphylactic Reactions Safety Population

Subject ID	Treatment Arm	AE ID Number	Onset Date/Time (Study Day)/ Resolution Date/Time (Study Day)	Type of Reaction	Severity grade for the Symptom with Highest Severity	Onset Time for Highest Severity	Leading to IP Discontinuation?
XXXXX	XXXX	X	DDMMMYYYY/HH:MM (X)/ DDMMMYYYY/HH:MM (X)	XXXX	XXXX	/HH:MM	Yes
		X	DDMMMYYYY/HH:MM (X)/ DDMONYYYY/HH:MM (X)	XXXXX			No
		•••					
XXXXX	XXXX	X	DDMMMYYYY/HH:MM (X)/ DDMONYYYY/HH:MM (X)	XXXXX	XXXX	/HH:MM	No

[figure not shown]
AE = Adverse Event.

Note: Study Day is calculated relative to the date of first dose.

Programming Notes:

- Sort by Treatment Arm/ Subject ID / Onset Date/Time / Resolution Date/Time / Reaction Type.
- Keep sorting from eCRF: Urticaria, Pruritus, Rash, Flushing, Swollen lips, tongue, uvula and/or vulva, Dyspnoea, Wheeze-bronchospasm, Stridor, Hypoxia, Hypotension, Crampy abdominal pain, Vomiting, Diarrhoea, Other.

Final 1 2 | 04-Oct-2023 | Page 184 of 218

Listing 16.2.9.10 Liver Diagnostic Investigations Safety Population

Subject ID	Treatment Arm	Potential Hy's Law Case Number	Liver Diagnostic Investigation Date (Study Day)	Liver Diagnostic Investigation	Liver Diagnostic Investigation Results	Comments
XXXXX	XXXX	X	DDMMMYYYY (X)	XXXX	XXXX	XXXXX
		X	DDMMMYYYY (X)	XXXXX	XXXXX	
XXXXX	XXXX	X	DDMMMYYYY (X)	XXXXX	XXXXX	

[figure not shown]
CT = Computerized tomography; ERCP = Endoscopic retrograde cholangiopancreatography; MRI = Magnetic resonance imaging; MRCP = Magnetic resonance cholangiopancreatography.

Note: Study Day is calculated relative to the date of first dose.

Programming Notes:

- Sort by Treatment Arm/ Subject ID / Diagnostic Date / Liver Diagnostic Investigation.

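### Table 14.3.5.9 counts injection-site reactions only check by check, so the number of subjects per dose who ever reacted, and their worst grade, cannot be derived from it

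*SAP*

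**What the plan says.** The SAP file holds two sets of output shells, Draft 1.1 (31 August 2023) and Final 1.2 (4 October 2023).

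**Table 14.3.5.9, local injection site reactions, Safety Population.** For each time point the shell gives the number of subjects assessed. It then gives none, mild, moderate and severe counts for each of four signs, as percentages of the subjects in the group at that visit. The Draft 1.1 row header is "Day 1: 15 Minutes after Start of Infusion Subjects with injection Site Assessed". The Draft 1.1 programming note begins "Include the following timepoints: Day 1: 15 Minutes Post-Dose, Day 1: 30 Minutes Post-Dose, Day 1: 45 Minutes Post-Dose", adds a 1-hour check, and goes on "Day 1: 2 hours Post-Dose, Day 1: 4 hours Post-Dose, Week 2, Week 4" through to Week 18. The table names its source as "Reference Listing: 16.2.9.8".

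**Listing 16.2.9.8.** In both sets of shells the Day 1 checks are timed from the start of the infusion. The last two are "Day 1: 60 Minutes after Start of Infusion, Day 1: 4 hours after Start of Infusion". There is no 2-hour check.

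**Table 14.3.5.10, hypersensitivity and anaphylactic reactions.** The next table has a row for subjects with any such event and a block headed "Highest Severity Grade".

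**Final 1.2.** The visible part of Table 14.3.5.9 has the same layout. Its row labels are partly lost, and the end of the shell with its programming notes is not in the text available for review.

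**The concern.** Local tolerability by dose would normally be read from this table. The comparison wanted is how many subjects in each group reacted at all, and how badly. Counts at separate checks do not give this, because the same subject can appear at several checks and under several signs. A few subjects who react at every infusion and many who react once each can give the same printed rows.

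The labels are a smaller matter. The Draft 1.1 note uses a post-dose label where the row header and the listing count from the start of the infusion. Elsewhere in the same safety section a post-dose label appears to mean the end of the infusion: the vital-signs note lists a 5-minute post-dose reading on Day 1, and the footnote of that table says "Day 1: 5 minutes after Infusion Completion' time point was only applied to subjects enrolled in Stage 1". A programmer could therefore be unsure which origin is meant, and whether a 2-hour row belongs in the table.

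**Working it through.** The SAP gives no figure of its own to reproduce. The check is a count of rows, a bound, and a comparison of labels.

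**1. Size of the table**
- Draft 1.1 note: 15, 30 and 45 minutes and 1, 2 and 4 hours on Day 1 (6 checks), plus Weeks 2, 4, 6, 8, 10, 12 and 18 (7 checks). 6 + 7 = 13.
- Four signs per check: 13 × 4 = 52 separate blocks, of which 6 × 4 = 24 fall on Day 1.
- Visible rows that count a subject once across checks or across signs: none.

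**2. What the cells allow**

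For any set of cells in an arm of n subjects, the number of distinct subjects lies between the largest cell and min(n, sum of the cells).
- One later visit, one subject in each of the four sign cells: between 1 and 4 subjects with any sign.
- Day 1, one subject in each of the 24 cells, n = 26: between 1 and min(26, 24) = 24 subjects.

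**3. Illustration over the study**
- Arm size is an assumption. The footnote of Table 14.2.1.1.1 gives 106 subjects at Week 2. Four equal arms would give 106/4 = 26.5, so about 26. That is a modified intent-to-treat count and equal allocation is assumed, so it only approximates the Safety Population arms.
- Six infusions: Table 14.1.9 runs to six doses.
- Take one sign and one check per infusion visit, everyone assessed, and one reacting subject each time. Every visit prints 1/26 = 3.8%.
- If it is always the same subject, the share who ever reacted is 1/26 = 3.8%. If it is six different subjects, it is 6/26 = 23.1%.
- With 20 per arm the pair is 1/20 = 5.0% and 6/20 = 30.0%. With 35 it is 1/35 = 2.9% and 6/35 = 17.1%. The sixfold gap does not depend on the arm size.

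**4. Other places the number might appear**
- Listing 16.2.5.1 records for each infusion whether there was an injection-site reaction, but the exposure summary (Table 14.1.9) does not tabulate it.
- Listing 16.2.9.8 has no adverse event number, whereas the hypersensitivity listing, 16.2.9.9, has one. The shells therefore do not link these scores to the adverse event tables.

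**5. Labels**

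| Place | Day 1 origin | 2-hour check |
|---|---|---|
| Row header, Draft 1.1 | start of infusion | not applicable |
| Programming note, Draft 1.1 | post-dose | yes |
| Listing 16.2.9.8, Draft 1.1 and Final 1.2 | start of infusion | no |
| Programming note, Final 1.2 | not visible | not visible |

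The note has 13 time points and the listing 5 + 7 = 12; the difference is the 2-hour check. If post-dose were read as after the end of the infusion, the 15-minute check would fall at 15 + d minutes after the start, where d is the infusion length. The SAP text does not give d. For assumed lengths of 30, 60 and 120 minutes the results are 45, 75 and 135 minutes, against 15 under the header.

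**The case against.** **Per-visit tabulation is a choice, not an error.** The SAP treats other scheduled scores in the same way, for example the neuropathy sub-scores and the reflexes. Table 14.3.5.10 rests on an event listing, where any-event and worst-grade rows come naturally. If injection-site reactions are also reported as adverse events, Tables 14.3.1.2 and 14.3.1.3 count each subject once per preferred term, the latter at maximum severity. All this stands: nothing in the layout is stated wrongly, so the point is an improvement. But the SAP does not show that the scores feed the adverse event tables, and the scores are the data collected for this purpose.

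**The number is recoverable.** The listings hold subject-level scores with dates and times, and a single sign at a single later visit can be read directly. That is correct. The gap is in the table and not in the data.

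**The label conflict is in draft text.** A reader might infer that the final table will present checks made during the infusion as reactions persisting after it, and that their timing is lost. The documents do not support that. The conflicting note is in Draft 1.1 and its Final 1.2 counterpart cannot be seen. The reporting conventions say programming notes are not printed. The row label that would print, "Day 1: 15 Minutes after Start of Infusion", agrees with the listing. Assessment times (Listing 16.2.9.8) and infusion start and end times (Listing 16.2.5.1) let the timing be recovered. Nor would all three early checks necessarily fall within the infusion: with a 30-minute infusion, the 45-minute check is already outside it.

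**Conclusion.** The main point holds, at low weight. As far as its shells are visible, Table 14.3.5.9 does not give the number of subjects per dose who ever had an injection-site reaction, or their worst grade, and no other summary table is shown to supply it. The bound in the working needs no assumption. The 3.8% against 23.1% contrast is a constructed illustration resting on about 26 subjects per arm, equal allocation and full attendance. A row added in the unseen end of the Final 1.2 shell cannot be excluded.

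The label and 2-hour mismatch is real in Draft 1.1 but minor. In Final 1.2 only the listing can be seen, and it uses one origin throughout Day 1. Whether the conflict survives there is a question to check, not a finding.

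**What to change.** Add to Table 14.3.5.9, for each sign and for all four together, a row for subjects with any reaction at any time and a highest-severity-grade block, counting each subject once by treatment group. The denominator should be subjects with at least one injection-site assessment. Table 14.3.5.10 provides the format.

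Separately, check whether the Final 1.2 programming note still uses the post-dose labels and the 2-hour check. If it does, reconcile the row header, the note and Listing 16.2.9.8 against the eCRF, and use one label for each time origin.

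The cost is a change of shell wording and one extra block from data already collected. The table becomes slightly longer. No new data are needed and trial conduct does not change.

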Listing 16.2.9.17 - Prohibited Concomitant Medications - Safety Population	R				
Listing 16.2.9.18 - Concomitant Procedures - Safety Population	R				
Listing 16.2.9.19 - Anti-drug Antibody Test Results - Safety Population	U				
Listing 16.2.10.1 - Serum MEDI7352 Concentrations - PK Population					
Listing 16.2.10.2 - Serum total NGF Concentrations - PD Population	U				

Draft 1.1 | 31-Aug-2023 | Page 129 of 209

[figure not shown]

Listing Change Log:

Output Number	Date of Change	Change Made By (initials)	Description/Rationale

Draft 1.1 | 31-Aug-2023 | Page 130 of 209

Listing 16.2.1.1 Subject Disposition Screening Population

[figure not shown]
Subject ID	Re-screened?/ Previous Subject ID	Treatment Arm	Re-consent/ Date/Time of Initial IC/ Initial Protocol Version	Date/Time of Informed Consent	Protocol Version at consent/ Re-consent	Consent for Colsample? /Date of Consent	Consent for COVID-19 Sa fety Mea sures / Date of Consent	Current Protocol version
XXXX	No	XXXX	No	DDMMMYYYY/ hh:mm	XXXX	Yes/ DDMMMYYYY	Yes/ DDMMMYYYY	XXXXX
XXXX	Yes/ XXXX	XXXX	No	DDMMMYYYY/ hh:mm	XXXX	Yes/ DDMMMYYYY	Yes/ DDMMMYYYY	XXXXX
XXXX	No	XXXX	No	DDMMMYYYY/ hh:mm	XXXX	Yes/ DDMMMYYYY	Yes/ DDMMMYYYY	XXXXX
XXXX	No	XXXX	Yes / DDMMMYYYY/hh:mm / XXXX	DDMMMYYYY/ hh:mm	XXXX	Yes/ DDMMMYYYY	No	XXXXX
XXXX	No	XXXX	No	DDMMMYYYY/ hh:mm	XXXX	No	No	XXXXX

COVID-19 = corona virus disease 2019; IC = Informed Consent;

Programming Notes:

• Sort by Treatment Arm/ Subject ID.

Draft 1.1 | 31-Aug-2023 | Page 131 of 209

Listing 16.2.1.2 Assignment to Analysis Populations Screening Population

SubjectID	Treatment Arm	Screened [1]	Randomized	SAF [2]	mITT[3]	PK [4]	Reason to Exclude from Safety [5]	Reason to Exclude from mITT [6]
XXXXXX	XXXX	Yes	No	No	No	No		
XXXXXX	XXXX	Yes	Yes	Yes	Yes	Yes		
XXXXXX	XXXX	Yes	Yes	No	No	No	XXX	
XXXXXX	XXXX	Yes	Yes	Yes	Yes	Yes		
XXXXXX	XXXX	Yes	Yes	Yes	No	No	XXX/ XXX	XXX/ XXX

mITT = Modified Intent-To-Treat Population Set; NRS = numeric rating scale; PK = pharmacokinetics; SAF = Safety Population Set.

- If there is more than one major deviation, please concatenate with "/"
- Sort by Treatment Arm/ Subject ID.

^[1] The Screening Population includes all subjects who provide informed consent and provide demographic and/or baseline screening assessments.

[figure not shown]
^[2] The Safety Population includes all subjects who receive at least 1 dose of double-blind study medication.

^[3] The mITT Population includes all subjects in the Safety Population who have at least 1 daily NRS assessment while receiving double-blind treatment.

^[4] The PK Population includes all subjects for who a pharmacokinetic sample was obtained and analysed.

^[5] Major deviation reason/s to exclude from Safety Population for randomized subject.

^[6] Major deviation reason/s to exclude from mITT Population for randomized subject.

Listing 16.2.1.3 Reason for IP Discontinuation and Withdrawal from the Study Safety Population

[figure not shown]
Subject ID/ Treatment Arm	IP Discontinuation [1]/ Study Withdrawal	Completion/ Discontinuation Date (Study Day)	Date of Last Dose	Number of doses	Primary Reason for DC/ Withdrawal	Blind Broken? / Date/Time / Reason	Reason for breaking the Blind	Study Duratio n
XXXXXX/ XXXX	IP Discontinuation	DDMMMYYYY(XX)	DDMMMYYYY	XX	XXXXXX X	Yes / DDMMMYYYY/ hh:mm	XXXXXX	XX
XXXXXX/ XXXX	IP Discontinuation	DDMMMYYYY (XX)	DDMMMYYYY	XX	XXXXXX X	No		XX
XXXXXX/ XXXX	Study Withdrawal	DDMMMYYYY (XX)	DDMMMYYYY	XX	Other: XXXXXX X	No		XX

DC = Discontinuation; IP = Investigational product.

Note: Study Day is calculated relative to the date of first dose. Study Duration = Reference end date – date of first dose of treatment + 1.

- If reason for non-completion is Other, concatenate the specify text as follows: "Other: XXXXXXXXX".
- If reason for non-completion is adverse event, concatenate with AE line number as follows: "Adverse event number X".
- For Physician decision, screen-fail and withdrawal by subject, please provide explanation if presented on the logic "Physician decision: XXX".
- Do not include subjects who completed the study.
- Sort by Treatment Arm/ Subject ID.

^[1] Any withdrawal from the study before last IP dose (Week 10) is considered an IP discontinuation.

[figure not shown]
Listing 16.2.1.4 List of Reasons for Screening Failure Screen Failure Population

Subject ID	Treatment Arm	Screen failure Date	Primary Reason for Screen Failure
XXXXXX	Screen Failure	DDMMMYYYY	XXXXXXXX
XXXXXX	Screen Failure	DDMMMYYYY	XXXXXXXX
XXXXXX	Screen Failure	DDMMMYYYY	
XXXXXX	Screen Failure	DDMMMYYYY	Other: XXXXXXXXX
XXXXXX	Screen Failure	DDMMMYYYY	

Programming Notes:

- If reason for non-completion is Other, concatenate the "Primary Reason for Screen Failure" text as follows: "Other: XXXXXXXXX".
- Sort by Subject ID.

Draft 1.1 | 31-Aug-2023 | Page 134 of 209

Listing 16.2.1.5 Visits List and COVID-19 Impact Screening Population

Subject ID/ Treatment Arm	Visit Name	Visit Date (Study Day)	Is COVID- 19 Pandemic Ongoing?	Impacted by COVID-19	Was visit performed? / Visit Type	Visit Performe d Via	VS Data provided? / Assessments Missed?	IP dosing missed due to COVID-19 / Details	End of Treatment linked to COVID-19	Subject discontinued due to COVID-19?/ Details
xxxxx/ xxxx	Visit X	DDMMM YYYY (XX)	Yes	Yes	Yes/ Delayed	On site	Y/ Efficacy	Y/ XXXX	Other: XXXX	Y/ XXXX
xxxxx/ xxxx	Visit X	DDMMM YYYY (XX)	Yes	No	Yes		N/ Sa fety			
xxxxx/ xxxx	Visit X	DDMMM YYYY (XX)	No	Yes	Yes	Video	N/ Efficacy, Safety	Y/ Other: XXXX		
xxxxx/ xxxx	Visit X	DDMMM YYYY (XX)	No	No	No / Missed					

[figure not shown]
COVID-19 = corona virus disea se 2019; IP = Investigational Product; VS = Vital Signs.

Note: Study Day is calculated relative to the date of first dose.

Programming Notes:

- Visit Type: Missed, Abbreviated, Delayed.
- Visit Performed Via: Video, Phone, On Site Other: xxxxxx.
- Details on IP dosing missed: Treatment on hold due to Sponsor Decision, Subject infected with COVID-19, Subject decision, Other: xxxxxx.
- End of treatment, reason if due to COVID: Subject infected with COVID-19, Subject decision, Travel restrictions, Site closed, Study delayed/cancelled, Other: xxxxxx.
- Details on Subjects discontinuing due to COVID-19: Subject infected with COVID-19, Subject decision, End of Treatment due to Sponsor, Other: xxxxxx.
- Sort by Treatment Arm/ Subject ID/ Visit Date.

Draft 1.1 | 31-Aug-2023 | Page 135 of 209

[figure not shown]
Listing 16.2.2.1 Subjects Not Meeting All Inclusion Criteria or Meeting any Exclusion Criteria Screening Population

SubjectID	Treatment Arm	Enrolled	Randomized	Inclusion or Exclusion	Criteria Number	Criteria Label
XXXXXX	Screen Failure	Yes	No	Inclusion	XX	XXXXXXXXXXXXXXXXX
		Yes	No	Exclusion	XX	XXXXXXXXXXXXXXXXX

Programming Notes:

• Sort by Subject ID.

Draft 1.1 | 31-Aug-2023 | Page 136 of 209

[figure not shown]
Listing 16.2.2.2 Protocol Deviations Safety Population

						Covid- 19
SubjectIDTr	eatment Arı	n Analysis Population Event Date (Study Day)	Event Type	Description	Category	Related?
XXXXXX	XXXX	Screened\RND\SAF\DDMMMYYYY (XX) mITT	XXXXXXXXX	XXXXXXX	Non- important	Y
			XXXXXXXXXXXX	XXXXXXXXXXXXXX	-	
XXXXXX	XXXX	DDMMMYYYY (XX)	XXXXXXXXXX	XXXXXXXXXXXXXXXXXXXXXXXXXXXXXXXXXXXXXX	XXXXX	
			XXXXXXXXXXXXXXX	XXXXXXXXXX	XXXXX	
XXXXXX	XXXX	DDMMMYYYY (XX)	XXXXXXXXXX	XXXXXXXXXXXXXXXXXXXXXXXXXXXXXXXXXXXXXX	XXXXX	

COVID-19 = Corona virus disease 2019; mITT = Modified Intent-To-Treat Population; RND = Randomized Subjects; SAF = Safety Population. Note: Study Day is calculated relative to the date of first dose.

Programming Notes:

- The structure of this listing may change depending on the information in the protocol deviations file. In the analysis population column, include only the analysis population where subject is included in.
- o Sort by Treatment Arm/ Subject ID. If date is present in file, add a column for date of event and sort by date. If no date is present, sort by category with non-important first and then important.
- Event Type: Inclusion Criteria, Exclusion Criteria, Study Drug, Assessment Safety, Assessment Efficacy, Lab/endpoint data, Visit Window, Informed Consent, Prohibited Co-Medication, Overdose/Misuse, Other.

Listing 16.2.3 Randomization and Treatment group Safety Population

[figure not shown]
Subject ID	Treatment Arm	Randomization Stage	Randomization Treatment	Randomization Date / Time (Study Day)	Randomization Number
XXXXXX	XXXX	Stage 1	Active	DDMMMYYYY/hh:mm (-X)	XXXX
XXXXXX	XXXX	Stage 3	Active CC	DDMMMYYYY/hh:mm (-X)	XXXX
XXXXXX	XXXX	Stage 2	Placebo	DDMMMYYYY/hh:mm (-X)	XXXX
XXXXXX	XXXX	Stage 2	Active CC	DDMMMYYYY/hh:mm (-X)	XXXX
XXXXXX	XXXX	Stage 3	Placebo	DDMMMYYYY/hh:mm (-X)	XXXX

Note: Study Day is calculated relative to the date of first dose.

Programming Notes:

• Sort by Treatment Arm/ Subject ID.

Draft 1.1 | 31-Aug-2023 | Page 138 of 209

Listing 16.2.4.1 Demographic and Baseline Characteristics Screening Population

Subject	Treatment		Age (years)		Surgically sterile?/			Weight	Height	BMI	Fully vaccinated for COVID-
ID	Arm	Birth Date	[1]	Sex	Postmenopausal? [2]	Ethnicity	Race	(kg)	(cm)	(kg/m^2)	19?
XXX	XXX	DDMMMYYY	XX	XX		XXXXX	XXXX	XX.X	XX.X	XX.X	Y
XXX	XXX	MMMYYY	XX	XX	No/ Yes	XXXXX	XXXX	XX.X	XX.X	XX.X	N

COVID-19 = Corona virus disease 2019.

Note: Height and weight are the values at Screening.

[figure not shown]
[1] Age was calculated as age at time of consent.

[2] For Female Subject Only.

Programming Notes:

Sort by Treatment Arm/ Subject ID

Draft 1.1 | 31-Aug-2023 | Page 139 of 209

Listing 16.2.4.2 Medical History Safety Population

[figure not shown]
Subject ID	Treatment Arm	System Organ Class/ Preferred Term/ Verbatim Term	Start Date (Study Day)/ End Date (Study Day)/	
XXXXXX	XXXX	XXXXXXXXXXXXXX/ XXXXXXXXXXXXXX/ XXXXXXXX	DDMMMYYYY (X)/ DDMMMYYYY (X)	
		XXXXXXXXXXXXXX/ XXXXXXXXXXXXXXX/ XXXXXXX	MMMYYYY (X)/ Ongoing	
		XXXXXXXXXXXXXXXXXXXXXXXXXXXXXXXXXXXXXX	DDMMMYYYY (X)/ Ongoing	
XXXXXX	XXXX	XXXXXXXXXXXXXXXXXXXXXXXXXXXXXXXXXXXXXX	DDMMMYYYY (X)/ DDMMMYYYY (X)	

MedDRA = Medical Dictionary for Regulatory Activities. Note: Study Day is calculated relative to the date of first dose. Medical History were coded using MedDRA version 26.0. Only subjects with medical history recorded are listed.

Programming Notes:

- SOC & PT text should be in proper case in listing.
- Sort by Treatment Arm/ Subject ID / Start Date / End Date of medical event.

Draft 1.1 | 31-Aug-2023 | Page 140 of 209

Listing 16.2.4.3 Osteoarthritis Characteristics Screening Population

[figure not shown]
Subject ID	Treatment Arm	Subject with OA? / Joint/ Area affected	Is OA considered CS?	Radiological Investigations Conducted? / Details	Joint Area Investigated	Is OA considered RS?	K-L Score Reported	Radiologic Scoring System / Details/ Result
XXXXXX	XXXX	Y / Shoulder	Y	Y/ Other: XXXXXX	Shoulder	Y	Grade 3	XXXXXX/ XXXXXX/ XX
XXXXXX	XXXX	Y / Ankle	N	Y/MRI	Ankle	N	N	N

CS = Clinically Significant; K-L = Kellgren-Lawrence; OA = Osteoarthritis; RS = Radiologically Significant.

Programming Notes:

• Sort by Treatment Arm/ Subject ID

Draft 1.1 | 31-Aug-2023 | Page 141 of 209

[figure not shown]
Listing 16.2.5.1 Study Drug Administration: Individual Doses Safety Population

Subject ID/ Treatment Arm	Visit Name	Start Date/ Time (Study Day)	End Date/ Time (Study Day)	Was Infusion Performed?/ Infusion Volume (mL)[1]/ Reason not Performed	Actually Administered Volume (mL) [2]	If Difference between [1] and [2] Volume, Reason	Any Injection Site Reactions?	Any Infusion Related Reactions	Infusion Rate (mL/ hour)	Rate Change Justification	Reason for Infusion Rate Change
XXXX/ XXXX	XXX	DDMM MYYYY /hh:mm (X)	DDMM MYYYY /hh:mm (X)	Y/ XX	XX				xx.x		
XXXX/ XXXX	XXX	DDMM MYYYY /hh:mm (X)	DDMM MYYYY /hh:mm (X)	Y/ XX	XX	XXXXX	Y	Y	xx.x	XXXXX	XXXXX XX
XXXX/ XXXX	XXX			N/ XXXXXX							

Note: Study Day is calculated relative to the date of first dose.

Programming Notes:

- Sort by Treatment Arm/ Subject ID / Start Date / End Date.
- Rate Change Justification: Increased, Decreased, Interrupted.

Listing 16.2.6.1 Daily Pain NRS mITT Population

[figure not shown]
Subject ID	Treatment Arm	Study Visit [1]	Subject Diary (ePRO) Date / Study Day	Baseline Flag [2]	DPS
XXXXXX	XXXX	Baseline	DDMMMYYYY/ (-7)	Y	X
		Baseline	DDMMMYYYY/ (-6)	Y	XX
		•••	•••	•••	•••
		Baseline	DDMMMYYYY/ (-2)	Y	XX
		Baseline	DDMMMYYYY/ (-1)	Y	XX
		•••			
		Week 2	DDMMMYYYY/ (13)		XX
		Week 2	DDMMMYYYY/ (14)		XX
		•••			
		Week X	DDMMMYYYY/ (X)		XX
		•••	•••		
XXXXXX	XXXX	Baseline	DDMMMYYYY/ (-7)	Y	XX
DDG D 1 D				•••	•••

DPS = Daily Pain Score; ePRO = Electronic Patient-Reported Outcome; NRS = Numeric Rating Scale.

Note: Data shown in column 'DPS' are average daily pain scores on an 11-point (0-10) NRS. Study Day is calculated relative to the date of first dose. [1] Study Visit is defined as the 7-day period ending within the protocol window Day ± 3 , where at least 4 days out of 7 have recorded diary pain scores.

Draft 1.1 | 31-Aug-2023 | Page 143 of 209

^[2] Baseline is defined as the 7-day period prior to randomization i.e., Day -7 to Day -1, inclusive. A subject is considered to have an evaluable baseline pain score if there are at least 4 days of recorded diary pain scores in the 7-day period.

[figure not shown]

Programming Notes:

- Sort by Treatment Arm/ Subject ID / Subject Diary Date.
- Display all measurement per Subject, starting on the Study Day = -7.
- Display Study Visit for days involved in weekly averages of the average daily pain scores for Baseline, Week 2, 4, 6, 8, 10, and 12
- Flag Baseline records only when there is at least 5 days of recorded diary pain scores in the 7-day Baseline period

Draft 1.1 | 31-Aug-2023 | Page 144 of 209

Listing 16.2.6.2 Galer NPS mITT Population

Subject ID	Treatment Arm	Parameter	Study Visit	Collection Date / Study Day	Baseline Flag [1]	NPS
XXXXXX	XXXX	Pain intensity	Baseline	DDMMMYYYY/ (X)	Y	XX
			Week 4	DDMMMYYYY/ (X)		XX
			Week 8	DDMMMYYYY/ (X)		XX
				•••		XX
			Week X	DDMMMYYYY/(X)		XX
						XX
		XXXX	Baseline	DDMMMYYYY/ (X)	Y	XX
		•••		•••	•••	•••
XXXXXX	XXXX	Pain intensity	Baseline	DDMMMYYYY/ (X)	Y	XX
			•••	•••	•••	•••
		XXXX	Week X	DDMMMYYYY/ (X)		XX
		•••				

[figure not shown]
NPS = Neuropathic Pain Scale; NRS = Numeric Rating Scale.

Note: Data shown in column 'NPS' are Pain Intensity, Unpleasantness, and Descriptor scores on an 11-point (0-10) NRS, and Pain Duration/Frequency on a 3-point NRS (1-3).

Study Day is calculated relative to the date of first dose.

[1] Baseline is defined as the last observation recorded prior to the first dose of treatment.

Draft 1.1 | 31-Aug-2023 | Page 145 of 209

[figure not shown]

Programming Notes:

- Sort by Treatment Arm/ Subject ID / Parameter / Collection Date.
- Keep Parameter sorting from the last bullet point in this programming notes.
- Include all observed data on Galer NPS scores for Baseline, Week 4, 8, 12, and 18.
- Repeat for the Parameters: Pain intensity, Pain Unpleasantness, Pain Sharpness, Pain Hotness, Pain Dullness, Pain Coldness, Pain Sensitivity, Pain Itching, Deep Pain Intensity, Surface Pain Intensity (All in an 11-point NRS), and Pain Duration/Frequency (in a 3-point NRS).

Draft 1.1 | 31-Aug-2023 | Page 146 of 209

[figure not shown]

Listing 16.2.6.3
DSIS
mITT Population

Programming Notes:

- Same shell as Listing 16.2.6.1.
- Update footnote as:
 - DSIS = Daily Sleep Interference Scale; ePRO = Electronic Patient-Reported Outcome; NRS = Numeric Rating Scale. Note: Data shown in column 'DSIS' are daily Sleep Interference scores on an 11-point (0-10) NRS. Study Day is calculated relative to the date of the day of first dose.
 - [1] Study Visit is defined as the seven-day period ending within the protocol window Day ± 3 .
 - [2] Baseline is defined as the seven-day period prior to randomization i.e., Day -7 to Day -1,.
- Sort by Treatment Arm/ Subject ID / Subject Diary Date.
- Display all measurement per Subject, starting on the Study Day = -7.
- Display Study Visit for days involved in weekly averages of the average Sleep interference scores for Baseline, Week 4, 8, 12, and 18.

Draft 1.1 | 31-Aug-2023 | Page 147 of 209

Listing 16.2.6.4 SF-36 mITT Population

Subject ID	Treatment Arm	Parameter	Item Number	Item name	Study Visit	Collection Date / Study Day	Baseline Flag[1]	SF-36
XXXXXX	XXXX	Physical functioning	3	Vigorous Activities	Baseline	DDMMMYYYY/ (X)	Y	XX
					Week 12	DDMMMYYYY/ (X)		XX
			4	Moderate Activities	Baseline	DDMMMYYYY/ (X)	Y	XX
		•••	•••	•••	•••			
			-	Total	Baseline	DDMMMYYYY/ (X)	Y	
					Week 12	DDMMMYYYY/ (X)		XX
XXXXXX	XXXX	Role limitations due to physical		Cut Amount of Time Spent on Work/Act	Baseline			
		health	13	WOIK/ACt		DDMMMYYYY/(X)	Y	XX
					Week 12	DDMMMYYYY/ (X)		XX
			•••		•••	•••		•••
		•••			•••		•••	

[figure not shown]
SF-36 = 36-Item Short-Form Health Survey; NRS = Numeric Rating Scale.

Note: Data shown in column 'SF-36' are derived SF-36 scores and Change in General Health on a 5-point NRS (1-5).

Study Day is calculated relative to the date of first dose.

[1] Baseline is defined as the last observation recorded prior to the first dose of treatment.

Draft 1.1 | 31-Aug-2023 | Page 148 of 209

[figure not shown]

Programming Notes:

- Sort by Treatment Arm/ Subject ID / Parameter / Item /Collection Date.
- Keep Parameter sorting from the last bullet point in this programming notes.
- Include all data on SF-36 scores for Baseline and Week 12.
- Repeat for the Parameters: Physical functioning (items 3, 4, 5, 6, 7, 8, 9, 10, 11, 12), Role limitations due to physical health (items: 13, 14, 15, 16), Role limitations due to emotional problems (items: 17, 18, 19), Vitality (Energy/fatigue) (items: 23, 27, 29, 31), Emotional well-being (items: 24, 25, 26, 28, 30), Social functioning (20, 32), Pain (items: 21, 22) and General Health (items: 1, 33, 34, 35, 36), all with values ranging from 0 to 100. Change in general Health (in a 5-point NRS, item: 2).

Draft 1.1 | 31-Aug-2023 | Page 149 of 209

Listing 16.2.6.5 Rescue Medication Usage mITT Population

Subject ID	Treatment Arm	ATC Class (Level 2)/ Preferred Name/ Verbatim Term	Primary Indication	Start Date (Study Day)/ End Date (Study Day)	Dose (unit)	Route	Frequency
XXXXXX	XXXX	XXXXXXXXXXXXXXXXXXXXXXXXXXXXXXXXXXXXXX	Painful Diabetic Neuropathy	MMMYYYY (-XX)/ DDMMMYYYY (-X)	XXXX unit	XXXXXXXX	XXXXX
	XXXX	XXXXXXXXX/ XXXXXXXXXXXXXX/ XXXXXXXXXXX	Painful Diabetic Neuropathy	MMMYYYY (-X)/ Ongoing	XXXX unit	XXXXXXXX	XXXXX
	XXXX	XXXXXXXXX/ XXXXXXXXXXXXXXX/ XXXXXXXXXX	Painful Diabetic Neuropathy	DDMMMYYYY (X)/ DDMMMYYYY (XX)	XXXX unit	XXXXXXXX	XXXXX

[figure not shown]
ATC = anatomical therapeutic chemical.

Note: Study Day is calculated relative to the date of first dose.

Medications were coded using WHO drug dictionary version vMar2023.

Programming Notes:

- ATC & Preferred Name text should be in proper case in table.
- Ensure proper WHO-DDE version is printed in footnote.
- Sort by subject, start date/time, end date/time, ATC level 2 & Preferred Name.
- If Dose unit, Route or Frequency is Other, display other specify text only (ie, do not display "Other: XXXXXX") but just "XXXXXX").
- Adjust footnotes for frequency and routes as needed.
- Sort by Treatment Arm/ Subject ID / Start Date / End Date (alphabetically for ATC Class Level 2 if same date for two medications

Listing 16.2.6.6 Patient Global Impression of Change mITT Population

Subject ID	Treatment Arm	Study Visit	Collection Date / Study Day	PGIC
XXXXXX	XXXX	Week 4	DDMMMYYYY/(X)	XXXXXXXX
		Week 8	DDMMMYYYY/(X)	XXXXXXXX
		Week 12	DDMMMYYYY/ (X)	XXXXXXX
		Week 18	DDMMMYYYY/(X)	XXXXXXX
XXXXXX	XXXX	Week 4	DDMMMYYYY/(X)	XXXXXXX
		Week 8	DDMMMYYYY/(X)	XXXXXXX
		Week 12	DDMMMYYYY/ (X)	XXXXXXX
